11.0 STATISTICAL CONSIDERATIONS

11.1. Review of Study Design

At enrollment, women will be randomized 1:1 to either the standard-of-care mental health services (screening, referral, etc.) plus the Youth Friendship Bench SA intervention or standard-of-care services alone. Participants receiving the Youth Friendship Bench SA will complete individual counseling sessions at Enrollment, Week 2 (option to be conducted remotely), Week 4, Week 8 (option to be conducted remotely), and Week 12. They will also be invited to participate in an in-person or virtual group-based session (between their Week 8 and 12 visits, with the exact timing depending on participant availability and participant accrual rate) focused on an economic empowerment activity like job and school applications. Participants in the standard-of-care arm will complete visits at Enrollment, Week 4, and Week 12. The co-primary outcomes are: 1) the proportion with PrEP adherence measured by TFV levels detected in urine using a POC assay at Week 12 and 2) the proportion with reduced symptoms of common mental disorders measured by the SRQ-20 at Week 12. For the PrEP adherence measure, we will utilize urine TFV levels to assess PrEP dosing in the prior 4-7 days. The assay uses a threshold

of 1500 ng/mL to categorize participants as adherent as this was associated with daily dosing over 4-7 days in directly observed therapy.¹¹²

We will conduct all randomizations using a SAS-based computer-generated randomization scheme developed by the study data manager. The site sub-investigator will conduct the randomizations and fill out a randomization log which will be reviewed by the study data manager during visits to the study site. The identity of participants in each of the arms will not be known to investigators and access to the randomization code will be strictly controlled. The study blind will be broken only on completion of the clinical study and after the database has been locked. The study investigators will receive the unblended results only after that point.

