7.4. Co-Enrollment Guidelines

We will ask all potential participants to disclose their involvement in any other HIV or mental health (psychotherapy or pharmacotherapy) interventions at screening. The investigator team will make decisions about enrollment eligibility for those in other HIV or mental health studies on a case-by-case basis, depending on the type and level of service received and the likelihood of it interfering with Youth Friendship Bench SA delivery or primary outcome assessment.

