8.2. Lay Counselor Training and Supervision

Training: All Youth Friendship Bench SA counseling sessions will be conducted by one of two lay counselors, young women between approximately 24-30 years of age. These lay counselors will be trained by the protocol team during a one-week intensive training and will receive weekly in-person supervision by the study's research psychologist (**Appendix 3**). The training materials were developed and tested by the Friendship Bench team in Zimbabwe and have been used in a number of Friendship Bench adaptations globally.^{95,96,105} They include didactic sessions on common mental health conditions, symptom identification including screening tools like the SRQ-20, person-centered counseling skills, active listening, and problem-solving therapy techniques. The training is also designed to include time for practicing counseling skills throughout the week and to provide space for counselors to process their own feelings and stressors during the training. We will adapt the training materials as needed to ensure they are appropriate for young lay counselors in our population.

Supervision: Counselors will keep a progress note for the session. Sessions may be audiorecorded to ensure fidelity to the counseling messages and these audio-recordings will be reviewed with study team members in the US for remote supervision meetings with the counselors and the study team on a monthly basis. Participants will be asked whether they consent to having their counseling sessions audio-recorded as part of the enrollment consent process and will be informed that they can withdraw their consent for recording at any time. The study research psychologist will also conduct in-person supervision meetings with the counselors on a weekly basis, to discuss counseling progress, troubleshoot any difficult cases, and process any feelings of their own that are brought up during the counseling sessions.

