8.3.2. Screening and Enrollment Visit

The screening and enrollment visit may be conducted as a split visit as needed. Young women who are eligible and agree to study participation will be consented for 3 months of follow-up. The following procedures will take place:

- 1. Review and obtain written informed consent.
- 2. Confirm/Record locator information and phone number and contact preferences.
- 3. Assign a unique study identification number
- Assess eligibility (e.g., age 18-25 years, newly initiating PrEP at the clinic, symptoms of common mental disorders), including Adult Primary Care Guidelines screening questions and the SRQ-20
 - a. If participants report suicidal ideation or intent, have untreated or severe somatic symptoms or have other active psychiatric symptoms (e.g., hallucinations) the participant will be referred for assessment by a trained health professional (see Section 4.2).

Participants that are already on treatment with stable symptoms may continue to randomization.

- 5. Offer enrolment to eligible participants and refer ineligible for additional services if needed.
- Collect additional data on past mental history, participation in other mental health or HIV interventions, and other psychosocial and behavioral data (see Section 6).
- 7. Randomize participant to either Youth Friendship Bench SA intervention or the standard-of-care condition.
 - a. Participants randomized to the Youth Friendship Bench SA intervention will complete their first counseling session at this visit.
 - i. Collect preferences for SMS appointment reminders (see Section 4.3)
 - ii. Schedule participant for their Week 2 visit in 14 days. They will be offered the option to complete the Week 2 visit in-person or remotely (over the phone).
 - Standard-of-care participants will be scheduled for their next clinic visit at Week 4 in 30 days. They will not receive appointment reminders or remote services.

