10.0 DATA COLLECTION

10.1. Quantitative data collection

Demographic and behavioral data will be collected, including information on symptoms of common mental disorders, drug and alcohol use, GBV, post-traumatic stress symptoms, coping behavior, self-esteem, sexual relationship power, and sexual behavior (e.g., number of partners, vaginal sex with partners).

We will access the participant's clinic record to obtain information on age, HIV status, and PrEP status at screening. We will also abstract information on PrEP refills (bottle dispensed, dates of dispensation, and PrEP terminations) from the clinic records during the participant's three-month follow-up period.

Symptoms of common mental disorders will be assessed using the SRQ-20, which will be interviewer-administered by the lay counselors at enrollment, Week 4, and Week 12. Data on depressive symptoms (using the Patient Health Questionnaire-9 [PHQ-9]), anxiety (the Generalized Anxiety Disorder questionnaire [GAD-7]), history of mental health conditions and

services received, drug and alcohol use, GBV, and post-traumatic stress symptoms will also be interviewer-administered on study Case Report Forms (CRFs). All other demographic and behavioral data will be self-collected by participants using a tablet application. Research staff will be available in the clinic to provide guidance and assistance in completing the questionnaire as needed. De-identified data will be collected using REDCap and stored on a secure server.

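### Section 11.1 says investigators will not know participants' arms until database lock, but the sub-investigator randomizes each woman and trial conduct reveals arm; only a blind on results by arm is feasible

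*Protocol*

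**What the plan says.** Protocol section 11.1 makes two blinding statements. On participants: "The identity of participants in each of the arms will not be known to investigators and access to the randomization code will be strictly controlled". On timing: "The study blind will be broken only on completion of the clinical study and after the database has been locked". It adds that investigators receive the unblinded results only after that point.

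Between the account of the computer-generated scheme and those statements, the same paragraph says: "The site sub-investigator will conduct the randomizations and fill out a randomization log which will be reviewed by the study data manager".

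Section 8.3.2, on the visit at which randomization takes place, says: "Participants randomized to the Youth Friendship Bench SA intervention will complete their first counseling session at this visit". On session recordings, section 8.2 says that "these audio-recordings will be reviewed with study team members in the US for remote supervision meetings".

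The SAP does not mention blinding or masking of anyone. The Schema's one use of the term open-label describes the PrEP the women accept, not the allocation to arms.

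**The concern.** A sub-investigator is an investigator. If that person assigns and records each arm, the sentence about investigators not knowing arms is untrue on its face. The rest of the trial's conduct spreads the knowledge further.

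What is at stake is how decisions and measurements made after randomization will be read. Section 8.3.8 lets the site investigator withdraw participants, and the mental health part of section 9.1 leaves early termination to the study team case by case. The SRQ-20 co-primary outcome is collected by interview. A reader who trusts section 11.1 would take the decisions as made without knowledge of arm, and might assume the same of the interview. None of them can be.

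A separate matter is whether the next assignment can be anticipated while eligibility is being judged. That is allocation concealment, not blinding, and section 11.1 treats the two together.

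**Working it through.** **1. The claim against the rest of the protocol.** The claim is that investigators do not know arms before database lock.

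| Place | What happens | Who learns the arm |
|---|---|---|
| 11.1 | Sub-investigator randomizes and keeps the log; data manager reviews it | Sub-investigator, data manager |
| 8.3.2 | Intervention women have session 1 at the enrollment visit; control women are booked for Week 4 | Staff at that visit |
| 8.3.3, 8.3.5 | Week 2 and Week 8 visits exist only in the intervention arm | Site staff |
| 8.4 | SMS reminders and missed-visit follow-up are for the intervention arm only | Staff who do them |
| 8.2 | Research psychologist meets the counselors weekly about cases | Supervisor |
| 8.2 | Recordings, where made, are reviewed monthly with US team members | Study team members present |
| 10.2 | Interview sample is stratified by arm during follow-up, with protocol team oversight | Interview team and those overseeing it |

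The first row contradicts the claim without help from the others. No section sets up a separate unblinded team, a firewall or a masked assessor.

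**2. What is measured or decided with arm known.** Section 8.2 has one of two lay counselors deliver every intervention session. Sections 8.3.6 and 10.1 have the lay counselors administer the SRQ-20 at Week 12 in both arms. The people who score this co-primary outcome therefore include those who delivered the treatment. The discretionary decisions in 8.3.8 and 9.1 come after randomization, when arm is known at the site.

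**3. What does not depend on arm being hidden.** Section 8.3.2 lists eligibility and the SRQ-20 as step 4, the enrollment offer as step 5 and randomization as step 7. Under section 7.4 participation in other studies is disclosed at screening. No arm exists at these steps, so the question there is only whether the next assignment can be predicted.

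**4. How predictable the next assignment is.** Inputs: 110 women, 1:1, randomly sized blocks of at most 10 (Schema). The plan gives no block sizes, so the mix is an assumption. The observer recalls every past assignment and always guesses the arm that is behind, choosing at random when the arms are level.

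For a complete block of size 2m, the expected number of correct guesses is m + [2^(2m) / C(2m, m) − 1] / 2.

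- Size 2: 1 + (4/2 − 1)/2 = 1.50
- Size 4: 2 + (16/6 − 1)/2 = 2.83
- Size 6: 3 + (64/20 − 1)/2 = 4.10
- Size 8: 4 + (256/70 − 1)/2 = 5.33
- Size 10: 5 + (1024/252 − 1)/2 = 6.53

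With sizes 2 to 10 equally likely: (1.50 + 2.83 + 4.10 + 5.33 + 6.53) / 30 = 20.29/30 = 67.6%. With sizes 4 to 10: 18.79/28 = 67.1%. With size 10 throughout: 6.53/10 = 65.3%. Simulating 4,000 lists cut off at 110 women gives 67.5%, 66.9% and 65.3%. A mix weighted to small blocks would be higher (blocks of 2 alone: 1.50/2 = 75%). The value of 50% applies to someone who knows no past assignments. Hiding the future list does not by itself bring staff who see past assignments down to it.

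**The case against.** The strongest reply is that section 11.1 can be honoured in a narrower sense. Investigators can be kept from seeing outcomes by arm until database lock, and nothing in the documents prevents that. This stands: a reader might infer that the trial has no blind of any kind, and the documents do not support that.

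Several other limits also stand:

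- **Supervision and recordings.** Weekly supervision is by the research psychologist, not the study team as a whole. Sessions may be recorded only with consent (8.2), and remote sessions are not recorded (12.1.4). Session review is therefore secondary evidence, and the sub-investigator's role carries the point.
- **Eligibility.** A reader might infer that section 11.1 presents eligibility decisions as blinded. Eligibility comes before randomization, so the blinding sentence says nothing about it. The section does promise control of the randomization code, and no breach is shown.
- **Who judges eligibility.** A reader might infer that the sub-investigator who holds the log also decides who enters. No section says so. Screening is by the lay counselor (8.1), co-enrollment decisions are by the investigator team (7.4), and 8.3.2 names no one for the final decision.
- **Harm after randomization.** Non-adherence is not a reason for withdrawal, reasons are recorded and final evaluations are sought (8.3.8). The SAP's primary analyses include all randomized participants. These rules limit the damage from unmasked decisions, but they do not make the decisions or the SRQ-20 interview masked.

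**Conclusion.** The participant-level blind claimed in section 11.1 does not exist. It is contradicted within its own paragraph and by visits, reminders, follow-up, supervision and sampling that depend on arm. Only a results-level blind is feasible. Withdrawal, early termination and the SRQ-20 interview should be read as unmasked.

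This conclusion rests on the text alone and needs no numerical assumption. The figure of about 67% belongs to the separate question of concealment. It assumes particular block sizes, perfect recall and a guess for every woman, so it is an upper-end predictability figure for that observer. It would be wrong to read it as a bias in either co-primary comparison: nothing in the documents shows that anyone uses such guesses, or that the person who sees all assignments judges eligibility.

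The correction should be made because the protocol claims a property its design lacks and the remedy is cheap.

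**What to change.** **Blinding.** Replace the blinding sentences in section 11.1, and put the same statement in the SAP. It should say that the trial is open-label for participants, counselors, the sub-investigator, supervisors and the study team, and that outcome results by arm are withheld from investigators until database lock. If the sponsor adopts it, add that the analyst is masked to arm labels until lock. Analyst masking would be new, since neither document provides for it now.

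**Allocation concealment.** Describe it in its own paragraph. Keep the order in section 8.3.2, and require that eligibility, the co-enrollment decision and the baseline SRQ-20 are entered and locked before the next assignment is released. The REDCap system named in section 10.1 could do this if its randomization function is enabled. Otherwise, use sealed sequential assignments.

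**Cost.** A wording amendment to two documents and a one-time set-up. No arm, endpoint, sample size or clinical rule changes. The trial can no longer describe its investigators as blinded. Some predictability will remain, because the lay counselors who screen women also deliver the intervention sessions and so see who was allocated to them.

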11.2. Endpoints

11.2.2. Primary Endpoint

The primary outcomes are: 1) urine TFV levels above 1500 ng/mL at 12 weeks and 2) SRQ-20 scores less than 7 at 12 weeks

11.2.3. Secondary Endpoints

- Urine TFV levels above 1500 ng/mL at 4 Weeks
- Correlates of PrEP adherence at 12 weeks, adjusted for study arm.
 - Covariate characteristics assessed at baseline and follow-up may include: Sociodemographic characteristics; sexual behaviors; gender-based violence (GBV); symptoms of common mental disorders; self-esteem; and level of engagement with the intervention.
- Correlates of common mental disorder symptoms at 12 weeks, adjusted for study arm.
 - Covariate characteristics assessed at baseline and follow-up may include: Sociodemographic characteristics; sexual behaviors; gender-based violence (GBV); symptoms of common mental disorders; self-esteem; and level of engagement with the intervention.
 - Qualitative factors that influence acceptability, feasibility, and appropriateness of the Youth Friendship Bench SA intervention
 - SAEs (including events that result in death, are life-threatening, require inpatient hospitalization or prolongation of existing hospitalization, and/or result in persistent or significant disability/incapacity) and adverse events of special interest (reports of selfharm or self-injury).

11.2.4. Exploratory endpoints

- Mediators and moderators of the Youth Friendship Bench SA intervention effect on PrEP adherence at 12 weeks
 - Covariate characteristics assessed at baseline and follow-up may include: Sociodemographic characteristics; sexual behaviors; gender-based violence (GBV); symptoms of common mental disorders; self-esteem; intervention acceptability, feasibility, and appropriateness; and level of engagement with the intervention.
- Mediators and moderators of the Youth Friendship Bench SA intervention effect on symptoms of common mental disorders at 12 weeks
 - Covariate characteristics assessed at baseline and follow-up may include: Sociodemographic characteristics; sexual behaviors; gender-based violence (GBV); symptoms of common mental disorders; self-esteem; self-reported PrEP

adherence; intervention acceptability, feasibility, and appropriateness; and level of engagement with the intervention.

11.3. Accrual, Follow-up, and Sample Size

We will randomize 110 AGYW in a 1:1 ratio to either our adapted intervention or standard-of-care mental health services over a 12-month study period (approximately 9-10 AGYW enrolled per month). Based on current levels of AGYW receiving PrEP at the public health clinic in Johannesburg, and reporting symptoms of common mental disorders and receiving referral services, we will likely need to screen approximately 18-20 AGYW per month to meet our enrollment targets. Based on prior PrEP studies with AGYW in this setting (HPTN 082, PrEP SMART, POWER), we expect to retain 85-90% of AGYW through three months of follow-up.

For our primary outcome of PrEP adherence, if we assume 40% PrEP adherence in the standard-ofcare arm (as was seen in the HPTN 082 trial with AGYW in this setting) and an alpha of 0.05, we will have 80% power to detect at least a 20% difference in the proportion with adherence between arms.

For our primary outcome of common mental disorder symptoms, if we assume 50% prevalence of symptoms of common mental disorders (again, as was seen in the HPTN 082 and PrEP SMART trials) and an alpha of 0.05, we will have 80% power to detect at least a 25% difference in the proportion with symptoms of common mental disorders between arms.

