Differentiated and timely individual-level behavioral interventions may be insufficient to address the adherence and persistence challenges of all oral PrEP users. Longer-acting PrEP formulations may also offer greater flexibility and higher coverage than daily oral PrEP for AGYW with adherence challenges to daily pill taking. However, long-acting PrEP formulations will still require PrEP clients to be engaged in care and return to the clinic for regular assessment and resupply.³⁵ Integrated, holistic, and person-centered health services that are responsive to both the physical and mental health needs of AGYW will be critical to ensure engagement and retention in long-acting biomedical HIV prevention products delivery.²⁸

Symptoms of common mental disorders are prevalent among AGYW in HIV endemic settings and are associated with multilevel drivers of HIV risk. Our newly published work shows that 20-50% of AGYW initiating PrEP have moderate-to-severe symptoms of common mental disorders.^{24,25,27,36} Determinants of common mental disorders include proximal (e.g., racial discrimination, food insecurity, GBV,) and distal (e.g., gender inequality) factors, often acting together to cause elevated risk of depression, anxiety, and stress among AGYW.^{37,38} Our recent PrEP studies with South African AGYW found that depression and stress symptoms are associated with low support, stigma, food insecurity, and GBV, and these symptoms persist over one year among 50% of AGYW initiating PrEP.^{27,39} Other studies with African AGYW also report associations between symptoms of common mental disorders, structural drivers of HIV risk (GBV, financial insecurity, stigma), and increased HIV incidence.^{40–44} The COVID-19 pandemic has exacerbated mental health issues, food and financial insecurity, and ability to access HIV prevention and treatment services globally and in South Africa, underscoring the critical need to intervene on these drivers of HIV risk.^{45–47}

Common mental disorders negatively impact PrEP adherence, despite regular PrEP counseling and access to a multilevel. DoH package of PrEP services. Mental health symptoms may mediate the relationship between individual, interpersonal, and contextual factors and PrEP

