7.3. Eligibility

7.3.2. Inclusion Criteria

Young women who meet all of the following criteria are eligible for enrolling in this study:

- Female 18-25 years of age at screening
- Documentation of symptoms of a common mental disorder, as evidenced by a score greater than or equal to 7 on the Self Reporting Questionnaire 20-item (SRQ-20)
- Willingness to enroll and be randomized to either the Youth Friendship Bench SA or standard-of-care mental health services
- Written informed consent (obtained from participant or participant's legal representative and ability for participant to comply with the requirements of the study.
- Able to verbally communicate in one or more study languages to ensure participation in the counseling sessions (English, isiZulu)
- Taking PrEP at the Ward 21 clinic, as determined by clinic records. PrEP provision will be conducted by the clinic following National PrEP Guidelines and will not be part of study-specific procedures.

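### The SRQ-20 power statement uses a cohort prevalence where it needs the Week 12 rate in women who all enter at 7 or above, and its 80% ignores the plan's own expected dropout.

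*Protocol*

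**What the plan says.** Protocol 11.3 fixes the size of the trial: "We will randomize 110 AGYW in a 1:1 ratio to either our adapted intervention or standard-of-care mental health services". For the mental health co-primary it reasons "if we assume 50% prevalence of symptoms of common mental disorders", adds that this is the level "as was seen in the HPTN 082 and PrEP SMART trials", and concludes that "we will have 80% power to detect at least a 25% difference in the proportion with symptoms of common mental disorders between arms". Alpha is 0.05, with no statement of sidedness. The same section says "we expect to retain 85-90% of AGYW through three months of follow-up". The SAP repeats all of this under Sample size and Power calculations.

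Entry requires, in Protocol 7.3.2, "Documentation of symptoms of a common mental disorder, as evidenced by a score greater than or equal to 7" on the SRQ-20. The endpoint in Protocol 11.2.2 and SAP Co-Primary Analysis 2 is a score below 7 at Week 12, the same cut-off. The SAP estimates the effect as a relative risk from a Poisson model with arm as the only predictor.

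On the background rate, Protocol 5.1 reports that "20-50% of AGYW initiating PrEP have moderate-to-severe symptoms of common mental disorders". Protocol 5.1 and 5.2 put symptoms persisting over one year in HPTN 082 at 49-50%, counted among young women initiating PrEP. Section 5.2 adds that the earlier studies did not screen systematically for mental health.

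**The concern.** Because everyone starts at 7 or above, baseline prevalence in this trial is 100% by design. The control-arm rate that drives power is conditional: of standard-of-care women who start at 7 or above, how many are still there at Week 12? A prevalence among women starting PrEP, not selected on symptoms, answers a different question. If the conditional rate is never named, a reader cannot tell how much recovery under standard of care the design expects, or judge whether a 25-point gain on top of it is plausible.

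The second issue is independent of the first. The power sentence and the retention sentence sit in the same section, but the 80% does not appear to allow for the expected loss of 10-15% of participants.

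**Working it through.** **Inputs.** 110 women, 1:1, so 55 per arm (Protocol 11.3). Reference rate 50%, difference 25%, alpha 0.05, retention 85-90% (same section). Evaluable per arm: 55 × 0.90 = 49.5 and 55 × 0.85 = 46.75. I take alpha as two-sided. I read the difference as 25 percentage points, 50% versus 25%, because a relative 25% (50% versus 37.5%) gives only 26% power at 55 per arm.

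**Formulas.** With p1 and p2 the shares at 7 or above, p̄ their mean, and n per arm:

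- Pooled z: power = Φ{[|p1−p2|√n − 1.96√(2p̄(1−p̄))] / √[p1(1−p1)+p2(1−p2)]}
- Unpooled z: power = Φ{|p1−p2| / √[(p1(1−p1)+p2(1−p2))/n] − 1.96}
- Wald log-RR, with q = 1 − p the share below 7: power = Φ{|ln(q2/q1)| / √[(1−q1)/(nq1)+(1−q2)/(nq2)] − 1.96}

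**Step 1: the plan's own figure, everyone evaluable (n = 55).** Pooled: (0.25 × √55 − 1.96 × √(2 × 0.375 × 0.625)) / √(0.25 + 0.1875) = (1.854 − 1.342) / 0.661 = 0.774, so 78.1%. Unpooled: 2.803 − 1.960 = 0.843, so 80.0%. The stated 80% therefore reproduces with no dropout.

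**Step 2: same rates, expected retention (pooled).** At n = 49.5: (1.759 − 1.342) / 0.661 = 0.630, so 73.6%. At n = 46.75: (1.709 − 1.342) / 0.661 = 0.556, so 71.1%. Unpooled, the figures are 75.8% and 73.4%. On the analysis scale (RR = 0.75/0.50 = 1.50), Wald log-RR gives 2.471 − 1.960 = 0.511, so 69.5%, and 2.401 − 1.960 = 0.441, so 67.0%.

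**Step 3: change only the control rate, keeping 25 points.** The documents give no conditional Week 12 rate, so 50-90% is an assumed range.

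| SOC still ≥7 at Week 12 | Pooled, 55/arm | Pooled, 90% / 85% retained | Log-RR, 90% / 85% retained |
|---|---|---|---|
| 50% | 78.1% | 73.6 / 71.1% | 69.5 / 67.0% |
| 60% | 75.4% | 70.8 / 68.3% | 66.7 / 64.2% |
| 70% | 76.3% | 71.7 / 69.2% | 67.1 / 64.6% |
| 80% | 80.8% | 76.5 / 74.0% | 70.4 / 68.0% |
| 90% | 89.2% | 85.7 / 83.6% | 76.3 / 73.9% |

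**Step 4: separate the two effects (pooled).** Dropout alone costs 78.1 − 73.6 = 4.5 to 78.1 − 71.1 = 7.0 points. Moving the control rate from 50% to 60% costs about 3 points, moving it to 80% gains about 3, and moving it to 90% gains 11-13.

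**The case against.** The strongest reply is that the plan does assume something about standard-of-care recovery. Section 11.3 introduces the 50% for the Week 12 outcome and contrasts it between arms, so it implies that half of control women fall below 7. That stands: the assumption is present, but mislabelled and unsupported. It is also fair that the HPTN 082 figure is described as persistence, which is nearer to what is needed than point prevalence. It still counts all initiators and runs to one year.

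A reader might infer that true persistence must be well above 50%, since women with persistent symptoms are a subset of those with symptoms. The documents do not carry that to Week 12. They do not say that the earlier studies used the SRQ-20 at a cut-off of 7, and for PrEP SMART they give neither a symptom figure nor a denominator. The true rate could be near 50%.

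On retention, the SAP's intention-to-treat analysis covers all randomized women, with multiple imputation, and a Week 4 SRQ-20 is collected. Evaluable n is therefore an approximation. Imputation under missing-at-random recovers information only so far as observed data predict the missing score. I would expect that to be modest, but the documents give no correlation to test it.

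Sidedness matters too. A one-sided 0.05 test would give 83.1% and 81.1% at 90% and 85% retention. But it gives 86.4% with all 110, which is further from the stated 80%, and the SAP's table shells report 95% intervals, so two-sided is the natural reading.

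**Conclusion.** Two things hold. First, the 50% is not labelled or justified as the quantity the endpoint requires, namely the proportion of standard-of-care women at 7 or above at Week 12 among women all at 7 or above at entry. Second, the 80% assumes that all 110 are evaluable. At the plan's own retention the same inputs give 71-74% (pooled z, two-sided 0.05), or 67-70% on the relative-risk scale used in the analysis.

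It would be tempting to join these and say that the wrong control rate leaves the trial underpowered. The documents do not support that. With the difference held at 25 points, correcting the rate moves pooled power by about 3 points either way between 50% and 80%, and at 90% pooled power is 84-86% even after dropout. The shortfall at 50% comes from retention.

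This is an unsupported input plus a power figure that omits dropout; the arithmetic behind the 80% is sound. The sizes rest on a two-sided test, an absolute 25-point target, complete-case evaluable numbers, and an assumed 50-90% range.

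**What to change.** In Protocol 11.3 and the SAP's Power calculations:

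- Relabel the input as the assumed proportion of standard-of-care participants with SRQ-20 of 7 or more at Week 12, all being at 7 or more at entry.
- Drop the attribution to the earlier trials, or explain how their figures bear on that conditional 12-week rate.
- Replace the single 80% with power at 85-90% retention over a stated range of the rate, for example 50-90%. At 50% the entry would be about 71-74%.
- State that alpha is two-sided, if it is, and that the 25% is in percentage points.
- Optionally add power on the relative-risk scale (67-70% at 50%, Wald log-RR).

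The cost is wording in two places and a less favourable stated power. Sample size and design do not change.
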